parent(s)/LAR. The investigator must ensure that each participant and participant's parent(s)/LAR is fully informed about the nature and objectives of the trial and possible risks associated with participation. If the participant's parent(s)/LAR desires the participant to participate in the study and the participant wishes to participate in the study, an IRB-approved informed consent form will be signed and dated by the participant's parent(s)/LAR and a verbal or written assent from the participant will be collected (if applicable, as consistent with the participant's age and ability to provide assent), as required by the IRB. The informed consent and assent forms must be agreed by Pfizer and the IRB and must be in compliance with the International Council for Harmonisation (ICH) Good Clinical Practice (GCP), local regulatory requirements, and legal requirements.

The signed documents will be retained at the site, and the investigator or person designated by the investigator must document in the source documents that informed consent and assent were obtained.

The participant will be assigned a participant identifier after informed consent and assent are obtained.

Visit 1 (Day 1)

After informed consent and assent have been obtained, the following assessments will be performed during the study visit:

1. Collect participant demography and parent(s)/LAR's contact information.
2. Obtain medical and surgical history.
3. Review prior and concomitant treatments.
4. Confirm eligibility for the study based on inclusion/exclusion criteria.
5. Record height, leg length, and weight.
6. Handedness questionnaire: [Edinburgh Handedness Inventory \(EHI\)-short form \(Annex 4\)](#).
7. Place device under study and APDM devices on participant.
8. Walk on a GAITRite® walkway at participant's natural speed (3 rounds = ~20 feet x 3) and at varied speeds while wearing device under study and APDM system. Natural speed is participant's self-chosen pace and varied speeds includes participant's self-chosen slow pace ("Walk slow") for 3 rounds and fast pace ("Walk fast") for 3 rounds.
9. Walk on tile and carpet (3 rounds on each surface) at participant's natural speed while wearing device under study and APDM system.

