The proposed sample size for this study is approximately 39 participants in each cohort (approximately 13 in each age group). To the best of our knowledge, no relevant data has been published before to validate accelerometry-measured gait metrics against GAITRite® walkway or APDM in pediatric population. Using data from X9001198 study (healthy adult participants, ages 18-40 and 65-85 years), the Intraclass Correlation Coefficient (ICC) between gait speed obtained from the sensor data vs gait speed obtained from the reference comparator gait mat was 0.72 (when corrected for a systematic bias of 0.17 m/s). The ICC value for the null hypothesis is derived by using the median value of the lower bound of ICC for all gait metrics (8 spatial and temporal metrics). ICC_{null} was 0.27, range = [0, 0.66]. In order to reach ICC value of 0.72 with ICC_{null} value of 0.27 using a one-tailed test with alpha = 0.05 and power = 0.8 it is estimated that at least 17 participants will be needed. Therefore, approximately 20 adult participants (anticipating 15% attrition) are required for the validation analyses. Here, we double the amount to roughly 40 participants to account for potential higher variance in the healthy pediatric participants (ages 3 – 17). Since we have 3 age groups, each group will equally have 13 participants, which results in a total of 39 participants.

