- Mixed model regression analyses will be used to investigate the effect of device (e.g., GAITRite, APDM, Actigraph), and the interaction between device and task (normal/slow/fast speed walks) on each gait metric. The device, task, and their interaction will be fixed effects, and subject will be entered as random effect. Post-hoc t-tests might be performed between devices. Multiple comparisons, when necessary, will be performed using FDR. Age (or age group) and sex may be used as covariates in the models. The estimates for fixed effect parameters, standard errors, 95% CIs, and p-values, as well as the variance estimates for the random effect will be summarized. Results from all models will be presented in a table. Furthermore, Least Squares Means (LSMeans) together with their 95% CI will be calculated for each of the device-task combination (e.g. LSMean of GAITRite gait speed for normal walk task).

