**Table 9 Specific Endpoints and Analyses for Primary Objective (Cohort B)**

	Devices	Measurements/comparisons
At-home monitoring (~days 8-15)	Reference: GENEActiv Comparator: Panaromic Bracelet	Sleep, scratch, and wear time endpoints as listed in Section 3.1.2

Appropriate summaries and plots for each digital endpoint will be produced (colored by age group, if necessary) as follows:

- To model the correlation between endpoints by the Panoramic Bracelet (comparator) and the GENEActiv device (reference), mixed effects model with repeated measures will be used with Panoramic Bracelet endpoints as the response, GENEActiv endpoints, as fixed effects, subject as the random effect. Device proximity (categorical; Panaromic- vs GENEActiv-closer to wrist) and their interaction might be added as fixed effects,. Within the subject (i.e., days) compound symmetry will be considered in the model. If there is no interaction effect, the interaction term will be removed from the model. Subject will be entered as random effect. As a sensitivity analysis, device proximity and the subject nested within the device proximity may be considered as random effects. Age group may be used as covariates in the models. The coefficient estimations for the fixed effects and the corresponding p values and 95% CI will be reported.
- To model the difference between the Panoramic Bracelet endpoints and the GENEActiv device (reference) endpoints, mixed effects with repeated measures model will be used with the difference as the response. Age group and proximity of the device may be used as additional fixed effects in the models. Subject will be entered as random effect. Compound symmetry will be considered to model within subject variability. The estimates for fixed intercept and fixed effect (if available) and the corresponding p values and 95% CI will be reported.
- The Deming regression will be used to assess relationship of endpoints between the comparator and reference devices while taking into account of variations from the multiple measures. The fitted slope, intercept and their corresponding 95% CI will be

---

reported. Weighted Deming and Passing-Bablok regression may also be considered if deemed appropriate.

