### **6.3.6. To evaluate the effect of floor surface (carpet vs. tile) on gait metrics collected using ActiGraph and APDM devices.**

The effect of floor surface will be evaluated on gait metrics extracted from APDM and Actigraph worn on the lumbar position (Section 3.2., Table 4).

The following analyses and plots will be provided (see Table 10):

- Box and whiskers plots of gait parameters by floor type.
- The effect of floor type on gait parameters will be analyzed using paired tests (paired t-test or Wilcoxon Signed-rank test), and the effect size will be computed per device.
- Mixed model regression analyses will be used to investigate the effect of device (APDM vs Actigraph), and device by floor type (carpet vs tile) interaction. The device, floor type, and their interaction will be fixed effects, and subject will be entered as random effect. Post-hoc t-tests might be performed between devices. Multiple comparisons, when necessary, will be performed using FDR. Age (or age group) and sex may be used as covariates in the model. The estimates for fixed effect parameters, standard errors, 95% CIs, and p-values, as well as the variance estimates for the random effect will be summarized. Results from all models will be presented in a table. Furthermore, Least Squares Means (LSMeans) together with their 95% CI will be calculated for each device-floor-type combination.

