##### 6.4.2. To compare gait quality metrics collected using Panoramic Bracelet devices, APDM devices and GAITRite® walkway, during in-lab sessions.

The common endpoints are derived from the Panoramic Bracelet device with respect to GAITRite and APDM. Same analyses plan will be implemented as listed in Section 6.1 Primary Objective (Cohort A).

Additionally, Deming regression will be used to assess relationship of endpoints between the comparator and reference devices while taking into account of variations from the multiple measures. The fitted slope, intercept and their corresponding 95% CI will be reported. Weighted Deming and Passing-Bablok regression may also be considered if deemed appropriate.

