### 6.6.2. To evaluate the effect of floor surface (carpet vs tile) on gait metrics collected using Panoramic Bracelet and APDM devices.

The effect of floor surface will be evaluated on gait metrics extracted from APDM and Panoramic Bracelet devices (Section 3.3, Table 7). Same analyses plan will be implemented as listed in Section 6.3.6.

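### The gait mixed model in SAP 6.1 treats recordings of the same walk as sharing only a subject effect, so its device contrasts can have standard errors that are too large or too small

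*SAP*

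**What the plan says.** SAP 6.1 (Cohort A primary objective) lists a mixed model for each gait metric with three devices and three walking tasks (normal, slow, fast): "The device, task, and their interaction will be fixed effects, and subject will be entered as random effect". It will report estimates, standard errors, 95% CIs and p-values, "as well as the variance estimates for the random effect will be summarized". One random effect is named and no residual covariance. SAP 5.1 mentions MMRM for Cohort A but gives no structure either. Where the SAP intends a structure it states one: compound symmetry in 6.2.1 and AR(1) in 6.5.1.

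The same model recurs:
- SAP 6.3.6 (floor surface): "The device, floor type, and their interaction will be fixed effects, and subject will be entered as random effect".
- SAP 6.5.2 (SIMI against GAITRite) repeats the device-by-task form.
- SAP 6.4.2 carries it to Cohort B gait ("Same analyses plan will be implemented as listed in Section 6.1"), and SAP 6.6.2 to Cohort B floor surface ("Same analyses plan will be implemented as listed in Section 6.3.6").

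The protocol's Visit 1 list has the child cross the GAITRite walkway at natural speed and "at varied speeds while wearing device under study and APDM system". One walk therefore yields a reading from every device.

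For the at-home comparison in Cohort B, SAP 6.2.1 takes another route: "mixed effects with repeated measures model will be used with the difference as the response".

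**The concern.** A subject intercept captures only a child's overall level. Three other sources of variation are likely here:

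- **Subject-by-task.** Slow and fast are self-chosen paces in children aged 3 to 17, so children will change pace by different amounts. All devices see that change together, and it cancels when two devices are compared on one walk.
- **Subject-by-device.** A device's error for a given child can repeat from task to task.
- **Unequal device error.** A pressure mat, a six-sensor set and a single lumbar accelerometer need not be equally precise.

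The planned model puts all of this into one residual and uses it for every contrast. Within SAP 6.1 it is the only analysis that tests whether device bias changes with walking speed, and the only one that gives a device effect averaged over tasks. The first matters for a device meant for home use, where speed is not controlled. SAP 5.1 counts any p below 0.05 as significant, and FDR control cannot repair p-values that are individually wrong.

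**Working it through.** **The plan's own figure.** The documents give no figure for this model. The planning ICC used below comes from Protocol, Study Size: the ICC against "the reference comparator gait mat was 0.72 (when corrected for a systematic bias of 0.17 m/s" (adult gait speed). The sample size built on it reproduces. With k = 2 measurements per child, n = 1 + 2(zα + zβ)²k / [(ln C)²(k − 1)] and C = (1 + 2×0.27/0.73)/(1 + 2×0.72/0.28) = 0.2832. So n = 1 + 4×6.183/1.592 = 16.5, rounded up to 17, and 17/0.85 = 20.

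**Set-up.** Let s be the variance between subjects, w subject-by-task, d subject-by-device and e remaining error. There are T tasks, D devices and n = 39 children, with balanced data. The subject-only model's residual has expectation

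e + [D(T − 1)w + T(D − 1)d] / (TD − 1).

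| Layout | Pooled residual |
|---|---|
| 3 devices × 3 tasks (6.1, 6.4.2) | e + 0.75(w + d) |
| 2 devices × 2 floors (6.3.6, 6.6.2) | e + (2/3)(w + d) |
| 2 devices × 3 tasks (6.5.2) | e + 0.8w + 0.6d |

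The correct error terms are e for device-by-task, e + d for a device contrast within one task, and e + Td for the device contrast averaged over tasks. With equal device error it follows that:

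1. The device-by-task SE is too wide once w or d exceeds zero.
2. The within-task SE is too wide if w > d/3 (3×3), or w > d/2 (floor and SIMI).
3. The averaged SE is too narrow if d > w/3 (3×3 and SIMI), or d > w/2 (floor).

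A REML random-intercept fit gave the same residual variance as this pooled mean square.

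**Assumed inputs.** Subject SD 0.15 m/s (s = 0.0225); subject-by-task SD 0.05 to 0.10 m/s; 25% to 75% of device error variance repeating within a child. Total device error is set by (s + w)/(s + w + d + e) = 0.72.

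**Middle case (SD 0.10, 50%).** d + e = 0.0325×0.28/0.72 = 0.01264, so d = e = 0.00632. The pooled residual is 0.00632 + 0.75×0.01632 = 0.01856. Model SE divided by true SE:
- device-by-task: √(0.01856/0.00632) = 1.71
- within task: √(0.01856/0.01264) = 1.21
- averaged: √(0.01856/0.02528) = 0.86

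For a change in bias between two speeds, the true SE is √(4×0.00632/39) = 0.0255 and the model SE is √(4×0.01856/39) = 0.0436. The smallest change found with 80% power is (2.024 + 0.851)×0.0255 = 0.073 m/s with paired differences. With the planned model it is 1.968×0.0436 + 0.842×0.0255 = 0.107 m/s.

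**Lowest averaged ratio (SD 0.05, 75%).** d = 0.00729, e = 0.00243, pooled residual 0.00977. The ratio is √(0.00977/0.02431) = 0.63. The normal approximation gives a two-sided tail beyond 1.96×0.634 = 1.24, about 21%; simulation gave 22%.

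**Range over the assumptions:**

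| Layout | Interaction ratio | Averaged device ratio | False positives, averaged device |
|---|---|---|---|
| 3×3 gait | 1.2 to 2.4 | 1.01 down to 0.63 | 5% to 22% |
| 2×2 floor | 1.2 to 2.3 | 1.07 down to 0.73 | 4% to 15% |
| 2×3 SIMI | 1.2 to 2.3 | 1.01 down to 0.60 | 5% to 24% |

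In the 3×3 layout the within-task ratio is 1.00 to 1.24, and the interaction contrast rejects 1.6% down to 0.0% of the time instead of 5%.

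**Unequal device error alone** (w = d = 0; SD 0.11 for the test device, 0.03 for each reference). The pooled residual is (0.0121 + 0.0009 + 0.0009)/3 = 0.00463. The ratio is √(2×0.00463/0.0130) = 0.84, and false positives are about 10%, in all three test-versus-reference contrasts.

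**Without the ICC anchor** (s = 1, e = 0.1), the device F test rejected 0.0% of the time at w = 0.5, d = 0, and 36.6% at w = 0, d = 0.25.

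**Alternatives.** Paired differences gave 4.6% to 5.5% false positives in all 22 scenarios simulated, including unequal device error. A joint model with both interaction intercepts and device-specific residuals gave 3.6% to 5.5% in the three scenarios tried. The same two intercepts with a pooled residual left 8.5% to 9.6% under unequal device error alone.

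**The case against.** The strongest reply is that little of the primary objective depends on this model. The protocol's primary analysis is mean absolute percent error, Bland-Altman limits and ICC. No pass/fail rule uses the model's p-values, and SAP 5.1 already plans paired t-tests or Wilcoxon tests. This stands and limits the weight of the point. A within-task bias of 0.17 m/s would be found either way: in the middle case the model SE is √(2×0.01856/39) = 0.031, giving a ratio of 5.5.

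The LSMeans of each device-task cell also keep correct standard errors with balanced data and equal device error. In the 3×3 layout the estimated subject variance is s + 0.25(w + d), and adding the pooled residual returns s + w + d + e. This too stands; those standard errors go wrong only if device errors differ.

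The size depends on chosen inputs. An adult sensor-to-mat ICC is reused for children and for SIMI. The pace-change SD is reused for two floors both walked at natural speed; at 0.02 m/s the top device-by-floor ratio falls to 1.77, while the averaged ratio worsens to 0.67. With no repeating error and SD 0.05, all 3×3 ratios are 1.09. The ranges are therefore illustrations, not bounds. The direction rules do not depend on them.

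Change of bias with speed can be read from the per-task differences, but no other analysis in SAP 6.1 tests it. Finally, the planned Cohort A interim report (March 2023) precedes the current SAP (September 2023), so the change may fall after Cohort A has been analysed. That affects how it is documented, not whether the model is right.

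**Conclusion.** The concern holds. As written, the model in SAP 6.1 and its copies gives valid device contrasts only if subject-by-task and subject-by-device variances are both zero and device errors are equal, or if departures happen to cancel for a given contrast. With equal device error, the test of whether bias changes with speed is too conservative. The averaged device test can err either way, and over most of the assumed range it rejects too often. Unequal device error alone makes both reject too often. The true size in this trial cannot be known from the documents, and the ratios rest on the variance assumptions above.

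The affected outputs are standard errors, confidence intervals and p-values of device contrasts. Point estimates, per-task mean differences, agreement statistics, paired tests and the sample size stand. This should be corrected, but it does not undermine the primary agreement results.

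**What to change.** In SAP 6.1, 6.3.6 and 6.5.2, and by reference 6.4.2 and 6.6.2:

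1. Take device and device-by-task (or device-by-floor) contrasts from a model of the paired difference for each test-reference pair. Use task or floor type as fixed effect and an unstructured covariance across tasks within child, with a subject random intercept as fallback if that does not converge. The shared walk then cancels, and repeating device error is modelled.
2. If one joint model is kept for the LSMeans, add subject-by-task (or subject-by-floor) and subject-by-device random intercepts and device-specific residual variances. Drop a component only if it is estimated as zero or the model does not converge.
3. State that the paired per-task comparison governs if the two disagree.

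The cost is a line or two of model code per analysis, reusing the SAP 6.2.1 approach, plus occasional convergence or zero-variance problems for some metrics. No new data are needed. If Cohort A has already been analysed, rerun it and record the revision as a dated change, so that both cohorts use the same gait analysis.

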## 6.2. Primary Objectives (Cohort B):

### 6.2.1. To Evaluate the Panoramic Bracelet device and associated algorithms in the quantification of physical activity (eg sleep), scratch, and wear time, as compared to another accelerometry device (GENEActiv) during the at-home period.

The list of common device data and comparisons are listed in Table 9. We will compare endpoints related to wear time, sleep, and scratch between Panoramic Bracelet (comparator) and GENEActiv (reference), during the at home period (~ days 8-15).

**Table 9 Specific Endpoints and Analyses for Primary Objective (Cohort B)**

	Devices	Measurements/comparisons
At-home monitoring (~days 8-15)	Reference: GENEActiv Comparator: Panaromic Bracelet	Sleep, scratch, and wear time endpoints as listed in Section 3.1.2

Appropriate summaries and plots for each digital endpoint will be produced (colored by age group, if necessary) as follows:

- To model the correlation between endpoints by the Panoramic Bracelet (comparator) and the GENEActiv device (reference), mixed effects model with repeated measures will be used with Panoramic Bracelet endpoints as the response, GENEActiv endpoints, as fixed effects, subject as the random effect. Device proximity (categorical; Panaromic- vs GENEActiv-closer to wrist) and their interaction might be added as fixed effects,. Within the subject (i.e., days) compound symmetry will be considered in the model. If there is no interaction effect, the interaction term will be removed from the model. Subject will be entered as random effect. As a sensitivity analysis, device proximity and the subject nested within the device proximity may be considered as random effects. Age group may be used as covariates in the models. The coefficient estimations for the fixed effects and the corresponding p values and 95% CI will be reported.
- To model the difference between the Panoramic Bracelet endpoints and the GENEActiv device (reference) endpoints, mixed effects with repeated measures model will be used with the difference as the response. Age group and proximity of the device may be used as additional fixed effects in the models. Subject will be entered as random effect. Compound symmetry will be considered to model within subject variability. The estimates for fixed intercept and fixed effect (if available) and the corresponding p values and 95% CI will be reported.
- The Deming regression will be used to assess relationship of endpoints between the comparator and reference devices while taking into account of variations from the multiple measures. The fitted slope, intercept and their corresponding 95% CI will be

---

reported. Weighted Deming and Passing-Bablok regression may also be considered if deemed appropriate.

- For each day, accuracy of the sensor-derived metrics will be determined by computing the mean difference, mean absolute difference, variation of the difference, the mean percent error, the mean absolute percent error and the effect size between the Panoramic Bracelet device and GENEActiv (reference) device metrics.
- Box and whisker plots of digital metrics from the Panoramic Bracelet device and GENEActiv device will be plotted for each day.
- Bias, including the mean bias across days and bias from repeated measures, will be assessed by Bland-Altman plots and 95% limits of agreement between the Panoramic Bracelet device and GENEActiv device. Specifically, the following error measures will be computed: mean difference, lower and upper 95% limit of agreement. For assessing bias from repeated measures, both mean difference and 95% limits will be computed from the mixed effects model described above.
- Intra-class correlation coefficient (ICC) and its lower and upper confidence limits between metrics derived from the Panoramic Bracelet device and GENEActiv device will be computed, for mean/median/25% quantile/75% quantile across daily measures.
- Scatter plots of digital metrics from the Panoramic Bracelet device vs GENEActiv device with corresponding regression line and 95% CI will be plotted. The regression line and the 95% CI will be derived from the previous mixed effects model.

#### **6.2.2. To evaluate the participant's or caregiver's perception of wearability and comfort of Panoramic Bracelet device during the at home monitoring period.**

The Wearability/Comfort Questionnaire responses obtained during the at home period (Day 7+2) for the Panoramic Bracelet device will be summarized as frequency and percentages. Bar plots will be provided per question (might be stratified by age group).

Due to the ordinal nature of the responses, a 0 to 4 scale will be assigned to each option (i.e. 0 = strongly disagree, and 4 = strongly agree), except for questions 5 (“The device changes the way I move”) and 6 (“The device changes the way I behave”), where the order of the scale should be reversed (i.e. 0 = strongly agree, and 4 = strongly disagree) to be consistent with the ranking of other questions. The total score will be calculated by summing up numeric scales for each individual question, and summarized descriptively.

The Cognitive Debrief of Wearability/Comfort Questionnaire will be summarized as frequency and percentages when appropriate. Participant explanations entered as free text will be provided in a listing.

